## 4.3 EVALUATION OF THE EFFECTS ON PATIENT OUTCOMES

- Can robot-assisted early mobilization improve muscle strength and reduce muscle loss compared with the historical collective?
- Can robot-assisted early mobilization reduce the duration of ventilation?  
In addition, further questions will be addressed:
- Does robotic-assisted early mobilization result in changes in consciousness, pain, cognition, health perception, cardiocirculatory and respiratory function, other factors such as pressure ulcers, bowel emptying, insulin requirements, and duration of treatment?

For this purpose, the following outcome criteria of the patients are examined.

Primary outcome criteria	Physical function/muscle strength	Surveyed according to the MRC (Medical Research Council) classification on upper and lower extremity and using the FSS-ICU (32, 33) at discharge ICU.
	Parameters for the assessment of muscle deterioration	Muscle thickness of quadriceps femoris muscle (thickness quadriceps femoris muscle and cross sectional area rectus femoris muscle)  Muscle thickness of the diaphragm / Thickening fraction diaphragm  Diaphragm mobility at discharge ICU
	Ventilation time	Duration (d) of invasive ventilation

Secondary outcome criteria	Consciousness/ cognition/ pain/ health perception	Pain using the Visual Analog Scale (VAS) (before and after mobilization).  Delirium incidence using the CAM ICU (34): number of days without delirium.  Sedation level using the Richmond Agitation Sedation Scale (RASS)(35)  level of consciousness using the Glasgow Coma Scale (GCS) (36)  Health-related quality of life after 3 months using the SF-36 questionnaire (37)
	Hemodynamics	Blood pressure / catecholamine demand / heart rate / cardiac output / oxygen consumption
	Respiration	CPAx-respiratory function(38) / oxygenation index / lung ultrasound parameter
	Others	Intestinal evacuation (yes/no)  Decubitus (grade classification 1-4 according to Shea (39))  Lactate level before and after mobilization (if laboratory value available)  Insulin requirement
	ICU Scores	SOFA [39] / Apache II (40) / SAPS II (41)  Intensive care unit treatment duration / inpatient treatment duration

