## 8. METHOD AND PROCEDURE

Patients of the LMU Hospital will be included according to the inclusion and exclusion criteria (see 5.2. and 5.3.). All patients who are to be treated surgically and whose postoperative care is planned in the anesthesiological intensive care units will be screened according to the inclusion and exclusion criteria. If the expected duration of postoperative ventilation exceeds 48 hours and there are no contraindications, the patient is given an information session. This should be done preoperatively with awake patients who are able of giving consent. In case of consent, the patient will be included in the study.

In addition, within the scope of the experience of the mobilizing specialists, nurses, physiotherapists, and physicians will be included according to inclusion and exclusion criteria, who are predominantly assigned to the intensive care units of the LMU Hospital and from T2 onwards to the anesthesiological intensive care units.

With the start of robot-assisted early mobilization, the survey will be conducted within the framework of organizational feasibility. This is carried out by project staff and ward staff. The survey ends with the last robot-assisted mobilization.

[figure not shown]

Fig. 5: Detailed procedure of the study with examination times of the patients

All patients will receive a physical examination at different time points to assess physical functionality and muscle strength, as well as a sonographic examination of leg muscles, diaphragm, and lungs. These examinations should be performed on day -1 (preoperatively), on postoperative days 1,2,3, then once a week if the patient remains in the Intensive Care Unit, on day 28, on the day of discharge from the Intensive Care Unit, and on a follow-up examination approximately 3 months after discharge from the Intensive Care Unit. The follow-up examination should only take place if the patients present themselves at the LMU Hospital anyway due to medically indicated follow-up examinations (not study-related). Alternatively, patients can be asked about their condition by telephone (see Fig. 5).

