### 8.3. DATA COLLECTION EFFECTS ON PATIENT OUTCOMES

In this study, various interventions will be performed on patients. All invasive procedures performed on patients will be performed as routine procedures independently of the study in the Intensive Care Unit (ICU) according to medical indication. The following study-related procedures will be performed on the patients beyond the informed consent and documentation of patient-related data:

Patients will receive robot-assisted mobilization within the first 72 hours after admission to the Intensive Care Unit  $\geq 2$  x / day for 20 minutes, for a minimum of ten treatment cycles or seven days. Clinical-functional examination with collection of clinical scores and ultrasound parameters on day -1, 1,2,3, then once a week if continued in the Intensive Care Unit, day 28, day of discharge from the Intensive Care Unit, 3 months after study inclusion (within the data collection period) (39).

No other study-related burdens or risks arise for patients.

An overview of clinical and study-related measures is provided below:

Measure	Measure performed	Specification/ Invasiveness
Education and informed consent	Study-related	Noninvasive
Clinical examination to determine physical function	Study-related	Noninvasive

Sonographic examination of the lungs, diaphragm, and M. quadriceps femoris	Study-related	Noninvasive
Early mobilization, robot-assisted	Study-related	Non-invasive within the framework of the CE-certified indication for approval
Documentation of patient-related data	Study-related	Noninvasive

In addition, personal data, laboratory values from clinical routine and clinical data are recorded:

Domain	Parameters
1. Personal Data	
	Age, sex, height, weight
Diagnosis	Admission and progressive diagnoses
Therapy	Medications, infusion solutions
2. Laboratory diagnostic data	
	Parameters determined from the routine
3. Clinical data	
SOFA score (52) Apache II score (41) SAPS II score (40) RASS(31) VAS GCS (36) Decubitus score according to Shea (37)	Temperature, mean arterial pressure, heart rate, respiratory rate, Oxygenation index, Blood pH, Lactate, Bicarbonate, Operative status, Glasgow Coma Score Chronic conditions, export urine See Scores
Acute renal failure	AKIN-Stadium
Data Organ replacement	Renal replacement procedures, ECMO therapy
Advanced hemodynamic monitoring	Cardiac index, zvO2... (if advanced hemodynamic monitoring such as pulmonary catheter or PICCO is established)

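### The question is muscle loss, but the primary muscle criteria are status measures tied to ICU discharge with no reference to the scheduled day -1 examination, and a baseline is not assured for the historical controls

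*Protocol*

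**What the plan says.** Protocol Section 4.3 poses the question "Can robot-assisted early mobilization improve muscle strength and reduce muscle loss compared with the historical collective" and heads the ultrasound entry of its outcome table "Parameters for the assessment of muscle deterioration". Both describe a change. The items listed are quadriceps thickness, rectus femoris area, diaphragm thickness and thickening fraction, and, as the last line, "Diaphragm mobility at discharge ICU". Strength and function are rated by MRC grade and "using the FSS-ICU (32, 33) at discharge ICU". No item mentions a baseline or a change.

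Section 8 schedules the physical and sonographic examinations more widely: "These examinations should be performed on day -1 (preoperatively), on postoperative days 1,2,3, then once a week" while the patient stays in the ICU, and also on day 28, at ICU discharge and at about three months. Section 8.3 repeats this schedule and lists "Sonographic examination of the lungs, diaphragm, and M. quadriceps femoris" among the study-related measures.

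For the comparison group, Section 8 (Conventional early mobilization) takes the information from routinely collected data, and Section 7.2 rules out matching. Section 1 says that the outcomes are measured at different points in time. Section 9 plans graphs of the parameters over their course and leaves the group comparison to robust methods that it does not name.

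**The concern.** The question and the measure do not match. Muscle thickness at ICU discharge is the starting thickness minus what was lost up to that day, so two patients with the same loss can differ because one entered surgery with more muscle. Two patients with the same daily loss can differ because one left the ICU sooner. Neither difference answers the question asked.

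The design makes both likely. Starting muscle mass is balanced neither by randomisation nor by matching. ICU treatment duration is itself a listed outcome, and Section 2 cites evidence that early mobilization shortens it. The entry rules differ too: Section 7.2 requires an expected ventilation time above 48 hours for robot patients but an actual one for historical patients, which could by itself give the historical group longer stays. Patients who die in the ICU have no discharge value, and Section 4.3 does not say how they are counted.

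At stake is whether a difference in the ultrasound criteria can be read as less muscle loss and, for the controls, whether a change can be calculated at all.

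**Working it through.** The protocol gives no rate of muscle loss, standard deviation, baseline-to-discharge correlation or expected stay, so there is no figure of its own to reproduce on this point. All numerical inputs below are assumptions, except the group size of about 30 v 30 (Section 1).

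**1. Length of stay.** Assume the same daily loss in both groups, that is, no effect on the rate of loss.
- Simple product: 1% x 2 days = 2%; 2% x 5 days = 10%.
- Compounded, with discharge on day 7 v day 10: at 1% per day, 0.99^7 = 93.2% and 0.99^10 = 90.4%, a gap of 2.8 points; at 2% per day, 0.98^7 = 86.8% and 0.98^10 = 81.7%, a gap of 5.1 points.

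Expressing the outcome as change from day -1 does not remove this gap, because the change is still read on a day that differs between patients.

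**2. Starting muscle mass.** A baseline imbalance of b SD, with correlation rho between baseline and discharge, carries b x rho SD into a comparison of discharge values. The standard error of that comparison at 30 v 30 is sqrt(2/30) = 0.258 SD.
- b = 0.3, rho = 0.7: bias 0.21 SD; the two-sided 5% error becomes 13%.
- b = 0.3, rho = 0.9: bias 0.27 SD; the error becomes 18%.
- Chance alone gives a 95% range of ±1.96 x 0.258 = ±0.51 SD for the baseline difference. The unmatched historical design may add to that.

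**3. Precision, if both groups have a baseline.** The difference detectable with 80% power at two-sided 5% is (1.96 + 0.84) x 0.258 = 0.72 SD for the discharge value alone. Baseline adjustment multiplies the variance by 1 - rho^2; a change score multiplies it by 2(1 - rho), assuming equal SDs at both times.

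| rho | 1 - rho^2 | adjusted (SD) | 2(1 - rho) | change (SD) |
|---|---|---|---|---|
| 0.5 | 0.75 | 0.63 | 1.00 | 0.72 |
| 0.7 | 0.51 | 0.52 | 0.60 | 0.56 |
| 0.8 | 0.36 | 0.43 | 0.40 | 0.46 |

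**4. Data available in each group.** Robot patients have a planned day -1 scan and later scans. For historical patients, Section 8 offers routine records, while Section 8.3 classes the sonography as study-related. A day -1 scan is therefore not assured for controls, and possibly no scan is. If it is absent, step 3 does not apply to the group comparison and no change can be computed for that group.

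**5. Candidate fixed days.** The weekly examinations take place only while the patient remains in the ICU, so a first weekly visit would drop those discharged earlier. Day 28 is listed separately from that condition. Neither supplies a value for patients who have died.

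**The case against.** The strongest reply is that the protocol does not clearly fix a discharge-only, unadjusted value. Section 1 has these outcomes measured at several times; the row heading speaks of deterioration; a preoperative scan is scheduled; and Section 7.3 foresees regression with several unnamed independent variables, so a baseline covariate is not excluded. The choice between a change score and a covariate can also be left to an analysis plan.

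Much of this stands. A reader might infer that the protocol prescribes absolute values; it nowhere says so, and this is only a reading of raw measures listed without a baseline. A reader might also infer that ICU discharge governs every ultrasound item. The words close a table entry after diaphragm mobility; extending them to the other items is natural but not certain. If they do not extend, those items have no time point in Section 4.3, which equally needs settling. What the reply does not supply is any place where the primary criterion becomes a change or a baseline-adjusted value: Section 1 names no metric, and Section 9 uses the course for graphs.

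It can also be argued that a shorter stay with less muscle lost by discharge is part of the treatment's total effect. That is a fair reason to keep the discharge reading. In unmatched groups, however, a difference in stay need not come from the treatment.

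Finally, moving the primary reading to the first weekly visit may look like the obvious cure. It would replace dependence on length of stay by selection on length of stay.

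**Conclusion.** The point holds as a mismatch between question and outcome definition, and it should be corrected before analysis. The primary criteria do not refer to the day -1 examination that would turn a status into a loss, and the only time point stated for them varies by patient. For the historical group, the baseline, and possibly any ultrasound value, is not assured. Followed as written, the plan risks a group comparison of muscle loss that is confounded or cannot be made.

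The mismatch rests on the text of Section 4.3, on the wider schedule in Sections 8 and 8.3, and on the natural reading of the ultrasound entry. The sizes rest on assumed inputs: the 2-10% gap and the residual variance of 0.51 are illustrations, not estimates for this trial, and the variance gain helps a group comparison only if both groups have baselines. The documents do not support a claim that the comparison is biased by a known amount, nor that historical scans are definitely absent.

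**What to change.** - In Section 4.3, define the muscle outcomes as change from, or adjusted for, the day -1 value.
- Align Sections 1 and 4.3 on the time point, and state whether ICU discharge applies to every ultrasound item.
- Keep ICU discharge as a time point for the muscle and strength criteria. Report, by group, the day of measurement and the number of ICU deaths without a value.
- Add the scheduled day 28 value as a supportive fixed-time reading. Do not move the primary reading to the first weekly visit.
- Where routine records hold no comparable measurement for the historical patients, report the change within the robot group only and make no between-group claim on muscle loss.

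No new examination of robot patients is needed. The cost is more than wording, though: the muscle outcomes may lose their comparative claim, and some day 28 examinations will be missed after discharge. Day 28 also does not restore values for patients who have died.

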## 7.2 INCLUSION AND EXCLUSION CRITERIA FOR PATIENTS

### *Inclusion criteria*

- planned surgical intervention
- postoperative intensive care and therapeutic treatment
- expected duration of ventilation > 48 hours
- age ≥ 18 years
- preoperative patient consent for the study
- weight >45 kg and <135 kg

- Body height >1.50 m and <1.95 m

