#### *Exclusion criteria*

- Patients refusal to participate in the study
- unable to give informed consent
- chronically bedridden before inclusion
- clinical frailty scale  $\geq 7$  (42)
- chronic ventilation (more than 24 hours) before admission to the intensive care unit
- Elevated intracranial pressure / risk for elevated intracranial pressure / recent cerebral hemorrhage
- Pregnancy
- Pre-existing neuromuscular disease resulting in chronic limitation of strength and performance
- Sternotomy / Sternectomy during a surgical procedure

Patients meeting the following criteria will be retrospectively selected for the historical comparison group:

- planned surgical procedure
- Postoperative intensive care and therapeutic treatment
- Duration of ventilation > 48 hours
- age  $\geq 18$  years
- Weight >45 kg and <135 kg
- Body height >1.50 m and <1.95 m
- Patients who met any of the exclusion criteria during their intensive care unit stay will not be included in the historical group.

No matching is planned.

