#### Robot-assisted early mobilization

Patients included in the study according to the inclusion and exclusion criteria will be mobilized using the robotic system. The aim is to perform a standardized mobilization with verticalization within the first 72 hours after admission to the Intensive Care Unit. If possible, this should be performed twice every day for 20 minutes, with a minimum of ten treatment cycles or for seven days. Treatment characteristics such as timing, intensity, duration, and complications will be documented.

As part of the study, routinely collected personal data and laboratory chemistry data will also be documented. There will be no blood sampling or other invasive procedure as part of the study. The study period begins for the patients after their informed consent shortly before the surgical procedure and ends approximately 3 months after study inclusion with the planned follow-up examination, with the end of the recording period of the study or the death of the patient.

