Invasive ventilation	Duration, ventilation parameters, CPaX-respiratory function (39)

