## 9. BIOMETRY

In the context of organizational feasibility, descriptive data is reported and visualized for robot-assisted VEM. Subsequently, regression analyses are used to contextualize and quantify the data. Depending on the variables and the type of distribution, they are quantified after calculating degrees of freedom and correlations are tested using applicable analysis methods.

Descriptive data on stress experience and physical behavior will be collected within a robot-assisted mobilization situation and analyzed and visualized using descriptive statistics.

Within the study population, conventional early mobilization of critically ill intensive care patients (historical comparison group) will be compared with robot-assisted early mobilization. The data will be evaluated by graphical representations of the individual parameters in the course by means of box plots and scatter diagrams. Associations between parameters are quantified using appropriate (depending on scale level and distribution) correlation coefficients. For comparison between conventional and robot-assisted VEM, commonly used robust statistical methods are applied.

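### The primary ventilation outcome is raw days of invasive ventilation with no treatment of death and no mortality outcome beside it, so weaning and death cannot be told apart.

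*Protocol*

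**What the plan says.** Section 4.3 lists three groups of primary outcome criteria. The third, ventilation time, is defined in full as "Duration (d) of invasive ventilation". The research question in the same section is "Can robot-assisted early mobilization reduce the duration of ventilation", which fixes the favourable direction.

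The other relevant statements are:

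- **End of observation.** Section 8 (Robot-assisted early mobilization) ends the patient's study period at the follow-up about three months after inclusion, "with the end of the recording period of the study or the death of the patient".
- **Data collected.** For invasive ventilation, section 8.3 lists "Duration, ventilation parameters, CPaX-respiratory function". Neither the outcome table in 4.3 nor the data list in 8.3 contains mortality, vital status or ventilator-free days.
- **Comparison.** Section 9 says "For comparison between conventional and robot-assisted VEM, commonly used robust statistical methods are applied" and names no method for death.
- **Control group.** Section 7.2 takes it retrospectively from routine data and states "No matching is planned". The Executive Summary gives about 30 patients per group.
- **Entry.** Robot-group patients need "expected duration of ventilation > 48 hours". Historical patients need "Duration of ventilation > 48 hours", that is, ventilation that actually lasted that long.

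**The concern.** In a critically ill population some patients will die while ventilated. Their time on the ventilator ends, but not because they were weaned. If that time is entered as a duration, a patient who dies ventilated on day 3 has a smaller, nominally better value than a survivor weaned on day 8. A patient who dies ventilated on day 20 has a worse value than either. The group difference then depends on how many die and when, as well as on weaning.

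Randomisation would at least make equal mortality the expectation when treatment has no effect. An unmatched historical control does not, because case mix and period may differ. The entry rules add to this: a death on the ventilator within 48 hours can occur in the robot group but cannot appear in the historical group.

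With no mortality outcome planned, a reader shown a difference in ventilation days would have no planned figure to check it against. Section 10 says that superiority could lead to rapid adoption in routine care, so the reading of this outcome matters.

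**Working it through.** **Inputs from the protocol.** Outcome: days of invasive ventilation, shorter is better (4.3). Group size: about 30 and 30 (Executive Summary). The protocol states no mortality, mean, standard deviation or expected effect for ventilation time, so it has no figure of its own to reproduce here.

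**Assumed inputs.** Weaning time is the same in both groups: lognormal, median 6 days, log-SD 0.8, with values below 2 days set to 2. The share dying on the ventilator is 10% in one group and 20% or 30% in the other. Death times are uniform over days 2 to 10 (early) or days 2 to 28 (spread).

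**Step 1: mean weaning time.** (ln 2 - ln 6)/0.8 = -1.373. Mean S = 2 × Φ(-1.373) + 6 × exp(0.32) × Φ(0.8 + 1.373) = 2 × 0.085 + 8.263 × 0.985 = 8.31 days.

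**Step 2: shift with no true effect on weaning.** If a share p die with mean recorded duration D, the group mean is (1 - p) × S + p × D. The difference between groups is therefore (p2 - p1) × (D - S). It is negative when D is below S and positive when D is above S.

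**Step 3: values of D.** If the day of death is taken as the end of ventilation, D is the mean of the uniform: (2 + 10)/2 = 6 for early deaths and (2 + 28)/2 = 15 for spread deaths. If duration is the earlier of weaning and death, simulation gives D of about 4.5 and 6.6.

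| Deaths | Scoring | D | 10% v 20% | 10% v 30% |
|---|---|---|---|---|
| Days 2-10 | earlier of weaning and death | 4.5 | 0.1 × (4.5 - 8.31) = -0.4 | 0.2 × (4.5 - 8.31) = -0.8 |
| Days 2-10 | day of death | 6 | -0.2 | -0.5 |
| Days 2-28 | earlier of weaning and death | 6.6 | -0.2 | -0.3 |
| Days 2-28 | day of death | 15 | +0.7 | +1.3 |

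The first row corresponds to simulated means of 7.9 v 7.6 days and 7.9 v 7.2 days, so its second entry is about -0.7 from the rounded means. Deaths averaging day 3 would give 0.2 × (3 - 8.31) = -1.1 at 10% v 30%.

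**Step 4: against sampling error.** The simulated standard error of the difference in means with 30 per group is about 1.9 days for early deaths and 2.1 days for spread deaths scored at the day of death. The largest ratios are 0.7/1.9 = 0.37 and 1.3/2.1 = 0.62. By normal approximation, a two-sided 5% test would reject with probability Φ(-1.96 + 0.37) + Φ(-1.96 - 0.37) = 0.056 + 0.010 = 6.6%, and Φ(-1.96 + 0.62) + Φ(-1.96 - 0.62) = 0.090 + 0.005 = 9.5%. A simulated rank test in the early-death case rejected in 5.5% (10% v 20%) and 6.9% (10% v 30%) of studies.

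**Step 5: ventilator-free days on the same inputs.** Survivors average about 20 ventilator-free days to day 28. With death scored 0, the group mean is (1 - p) × 20: 18, 16 and 14 days at 10%, 20% and 30% mortality. The gaps are 2 and 4 days although weaning is identical, and rank-test rejection rises to about 9% and 26%.

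**The case against.** The strongest reply is that the protocol is silent here and sets no wrong rule. No section says how a death on the ventilator is scored. The end-of-study sentence in section 8 is a follow-up boundary for consented patients. It is not a scoring rule and says nothing of the historical group. Section 7.4 allows exclusion for incomplete data, so ICU deaths might instead drop out, which would be a different problem (a comparison among survivors). The handling of death is often left to a statistical analysis plan, and one may exist. Section 9 is open enough to admit a competing-risk analysis.

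Much of this stands. A reader might infer that the protocol counts an early death as short ventilation, so that a harmful device would look beneficial. The documents do not support that: the scoring is not stated, and the direction reverses when deaths are late. It also stands that every numerical input is assumed and that the artefact is well inside sampling error.

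What does not fall away is the choice of endpoint. The protocol itself names raw days as primary, gives a favourable direction and leaves mortality out of its outcome list, in a design where equal mortality cannot be presumed. An analysis plan can add a method, but the list of outcomes is fixed in the protocol.

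**Conclusion.** The concern holds as a problem of interpretability. As defined, a difference in ventilation days cannot be attributed to weaning, because deaths can move it either way and no planned outcome shows them.

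On the assumed inputs, the spurious shift lies between about -0.7 and +1.3 days and is at most about 0.6 of a standard error. It is unlikely by itself to produce a significant result with 30 per group. The protocol gives no mortality or ventilation data, so the true size and even the sign are unknown. The correction is worth making because it is cheap, but the study does not depend on it.

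A reader might also conclude that ventilator-free days must become the primary outcome because they point in the correct direction. That presumes the mortality difference is caused by treatment, which an unmatched historical comparison cannot show. With identical weaning, that outcome would turn a case-mix difference in mortality into a 2 to 4 day gap.

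**What to change.** - **Outcome and analysis.** In sections 4.3 and 9, analyse the ventilation outcome as time from a common origin to liberation from invasive ventilation, with death on the ventilator as a competing event. Show cumulative incidence curves for both events and a cause-specific hazard ratio for liberation. That ratio stays at 1 when weaning is identical and death is independent of it, as assumed above.
- **Origin.** Define it identically in both groups and say how the expected and actual 48-hour entry rules are aligned. One option is to start the clock at 48 hours among patients still ventilated. The cost is that earlier liberations and deaths in the robot group are described separately.
- **Mortality.** Add deaths by group, with timing and ventilation status at death, to the outcomes in 4.3 and the data list in 8.3.
- **Supportive results.** Report ventilator-free days to day 28 (death = 0) as a sensitivity analysis only, and raw duration as description.

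The cost is a change of wording, slightly more analysis work and the need to present both components together. No new patient contact is needed: the outcome data for the historical group already come from routine records, and ventilation times and deaths should be available there for both groups.
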